APPENDIX 3 REVISED INTERNATIONAL PROGNOSTIC INDEX (IPI) SCALE*

[figure not shown]
Composite score determined by assigning 1 point for each of the following factors;

- Age > 60 years
- ECOG PS > 2
- Elevated Serum LDH
- More than 1 extranodal site
- Stage III/IV disease (Ann Arbor staging)

APPENDIX 4 ECOG PERFORMANCE STATUS

ECOG PERFORMANCE STATUS^a	
0	Fully active, able to carry on all pre-disease performance without restriction
1	Restricted in physically strenuous activity but ambulatory and able to carry out work of a light or sedentary nature, eg, light house work, office work
2	Ambulatory and capable of all selfcare but unable to carry out any work activities. Up and about more than 50% of waking hours
3	Capable of only limited selfcare, confined to bed or chair more than 50% of waking hours
4	Completely disabled. Cannot carry on any selfcare. Totally confined to bed or chair
5	Dead

a 

APPENDIX 5 ACUTE GVHD GRADING AND STAGING

Table 1: Extent of Organ Involvement

Stage	Skin	Liver	Gut
1	Rash on < 25% of skin ^a	Bilirubin 2 - 3 mg/dL ^b	Diarrhea > 500 mL/day ^c or persistent nausea ^d
2	Rash on 25 - 50% of skin	Bilirubin 3 - 6 mg/dL	Diarrhea > 1000 mL/day
3	Rash on > 50% of skin	Bilirubin 6 - 15 mg/dL	Diarrhea > 1500 mL/day
4	Generalized erythroderma with bullous formation	Bilirubin >15 mg/dL	Severe abdominal pain with or without ileus
Grade ^e			
I	Stage 1 - 2	None	None
II	Stage 3 or	Stage 1 or	Stage 1
III	--	Stage 2 - 3 or	Stages 2 - 4
IV ^f	Stage 4	Stage 4	--

^a Use “Rules of Nines” (Table 2) or burn chart to determine extent of rash.

^b Range given as total bilirubin. Downgrade one stage if an additional cause of elevated bilirubin has been documented.

^c Volume of diarrhea applies to adults. For pediatric patients, the volume of diarrhea should be based on body surface area. Downgrade one stage if an additional cause of diarrhea has been documented.

^d Persistent nausea with histologic evidence of GVHD in the stomach or duodenum.

^e Criteria for grading given as minimum degree of organ involvement required to confer that grade.

^f Grade IV may also include lesser organ involvement with an extreme decrease in performance status.

Table 2: Percent Body Surfaces

Body Area	Percent	Total Percentage
Each Arm	9%	18%
Each Leg	18%	36%
Chest & Abdomen	18%	18%
Back	18%	18%
Head	9%	9%
Pubis	1%	1%

Stage of Chronic GVHD

Limited: Localized skin involvement resembling localized scleroderma with or without liver involvement; no other organ involvement.

Extensive: Generalized skin and/or multiple organ involvement.

## LIST OF FIGURES

[figure not shown]
Figure 2.1-1:	Study Design Schematic .....	10
---------------	------------------------------	----

For the ASCT-failed cohort, a two-stage design will be used to test whether nivolumab yields a clinically compelling objective response rate. In the first stage, responses will be evaluated by the IRRC on the first 37 subjects treated. If there are 8 or fewer responses in these 37 subjects, the study will be stopped. In this case, the study will be terminated in both the ASCT-failed cohort as well as the ASCT ineligible cohort. Otherwise, approximately 53 additional subjects will be accrued into the ASCT-failed cohort to target a total of 90 treated subjects. Recruitment and treatment of subjects in both cohorts (ASCT failed and ASCT ineligible) will continue as described during the evaluation of the first 37 ASCT failed subjects treated. The tolerability of the regimen will continue to be evaluated by the sponsor with the investigators to ensure that it is acceptable for continued enrollment. For the ASCT ineligible cohort a single stage design will be used to estimate the objective response rate using approximately 30 treated subjects.

**Figure 2.1-1: Study Design Schematic**

\* Recruitment and treatment of subjects in both groups (ASCT failure and ASCT ineligible) will continue as described during the evaluation of the first 37 ASCT failure subjects treated.

Note: Stage 1 data review will be conducted internally by BMS senior management for decision to proceed to second stage.

Subjects will undergo screening evaluations to determine eligibility within 28 days prior to first dose. Each 14-day dosing period will constitute a cycle. Radiographic study evaluations will take place in accordance with Table 2.1-1. A PET scan is required at baseline for all subjects, and to confirm a complete response (CR). Baseline assessments should be performed within 28 days prior to the first dose, utilizing spiral CT or MRI. An independent radiology review committee (IRRC) will also be utilized. The primary endpoint of this study is IRRC-assessed ORR, using the 2007 revised International Working Group Criteria for Malignant Lymphoma criteria. Secondary endpoints include IRRC-assessed duration of response (DOR), as well as complete remission rate (CRR), partial remission rate (PRR) and their duration and progression free survival (PFS) as determined by IRRC assessment and ORR based on investigator assessment.

Table 2.1-1: Schedule of Spiral CT/MRI Tumor Assessments			
Time On Study	Assessment Frequency	Assessment Week (day 1 of week shown)	Assessment Window
Dose 1 to 8 Months	Every 8 weeks	9, 17, 25, 33	+/- 1 week

Time On Study	Assessment Frequency	Assessment Week (day 1 of week shown)	Assessment Window
Month 9 to 2 Years	Every 12 weeks	45, 57, 69, 81, 93	+/- 2 weeks
> 2 Years	Every 6 months	119, 145, 171+	+/- 3 weeks

Note: Once subjects discontinue study therapy by proceeding to allogeneic SCT or ASCT, they will not undergo radiographic assessments as per the frequency described here, but will be followed using the following schedule. Tumor assessment (CR or non-CR) will be assessed by the investigator according to the 2007 IWG criteria and will be required on Day 100, at 6 months, 1 year and every year thereafter from the date of stem cell infusion until the first non-CR after SCT is documented.

## 2.2 Treatment Assignment

After the subject’s initial eligibility is established and informed consent has been obtained, the subject must be enrolled into the study by calling an interactive voice response system (IVRS) to obtain the subject number. Every subject that signs the informed consent form must be assigned a subject number in IVRS. Since this is a single arm study, all enrolled subjects who meet eligibility criteria will be treated with nivolumab at 3 mg/kg IV every 2 weeks.

## 2.3 Blinding and Unblinding

Not applicable

## 2.4 Protocol Amendments

This SAP incorporates the following protocol amendments.

**Table 2.4-1: Protocol Amendments**

Amendments	Date of Issue	Summary of Major Changes
Revised Protocol 02 (Incorporates Amendment 03)	23-Jul-2014	Allows for continued treatment of subjects in certain instances where protocol-defined progression criteria have been met. The amendment also serves to clarify various protocol requirements to ensure consistency in the execution of the study including secondary [REDACTED] and assessments to be performed on subjects that discontinue study treatment to receive an allogeneic SCT or ASCT
Revised Protocol 01 (Incorporates amendment 01)	06-Dec-2013	Per FDA mandatory recommendation: The protocol title and other sections have been updated to indicate that subjects who are not candidates for ASCT must

**Table 2.4-1: Protocol Amendments**

Amendments	Date of Issue	Summary of Major Changes
		
have failed at least 2 prior multi-agent chemotherapy regimens in order to meet eligibility requirements
 
Exclusion criteria have been added to exclude the following subjects
 
Subjects that have received chest radiation <math>\leq 24</math> weeks prior to first dose of the study drug
 
Subjects that received <math>\geq 1000</math> mg of carmustine (BCNU) as part of their pre-transplant conditioning regimen
 
Additional updates were also made to the protocol including items such as correcting typographical and formatting errors, including errors in the biomarker sampling schedule in Table 5.6-1

Original Protocol	30-Oct-2013	Not applicable

## 2.5 Data Monitoring and Other External Committees

An IRRC will be utilized in this study for determination of IRRC-assessed primary (ORR) and secondary (DOR, CRR, PFS) endpoints. The IRRC will review all available tumor assessment scans for all treated subjects. Details of IRRC responsibilities and procedures will be specified in the IRRC charter.

There will be no data monitoring committee for this study.

## 3 OBJECTIVES

### 3.1 Primary Objective

To assess the clinical benefit of nivolumab, as measured by independent radiologic review committee (IRRC) assessed objective response rate (ORR) in subjects with DLBCL or TL who are refractory or have relapsed following ASCT or after failure of at least two prior multi-agent chemotherapy regimens in ASCT ineligible patients.

### 3.2 Secondary Objectives

- To assess the duration of response (DOR) based on IRRC assessments
- To assess the complete remission rate (CRR) and the duration of CR based on IRRC assessment
- To assess the partial remission (PR) rate and the duration of PR based on IRRC assessment
- To assess progression free survival (PFS) based on IRRC assessment
- To assess the objective response rate (ORR), based on investigator assessments

[REDACTED]

[REDACTED]

[REDACTED]

[REDACTED]

#### 4 ENDPOINTS

##### 4.1 Primary endpoint ORR (IRRC-assessed)

The primary objective will be measured by the primary endpoint of IRRC-assessed objective response rate (ORR). It is defined as the number of subjects with a best overall response (BOR) of complete remission (CR) or partial remission (PR), according to the 2007 revised International Working Group Criteria for Malignant Lymphoma (see [Table 4.1-1](#)), divided by the number of treated subjects. The final analysis of the primary endpoint will occur at least 6 months after the last enrolled subject's first dose of study therapy (primary data lock time). The BOR is defined as the best response designation recorded between the date of first dose and the date of initial objectively documented progression per the 2007 revised International Working group Criteria for Malignant Lymphoma or the date of subsequent therapy, whichever occurs first. Stem Cell Transplant will be considered as subsequent therapy. For subjects without documented progression or subsequent therapy, all available response designations will contribute to the BOR determination. For subjects who continue treatment beyond progression, the BOR should be determined based on response designations recorded up to the time of the initial 2007 IWG defined progression. For purposes of analysis, if a subject receives one dose and discontinues the study without assessment or receives subsequent therapy prior to assessment, this subject will be counted in the denominator (as non-responder).

The IRRC-assessed objective response will be further characterized by the time to response (TTR). TTR is defined as the time from first dosing date to the date of the first response (CR or PR), as assessed by the IRRC.

**Table 4.1-1: 2007 IWG Response Criteria for Malignant Lymphoma**

Response	Definition	Nodal masses	Spleen, Liver	Bone marrow
CR	Disappearance of all evidence of disease	(a) FDG-avid or PET positive prior to therapy; residual mass of any size permitted if PET negative  (b) Variably FDG-avid or PET negative; regression to normal size on CT	Not palpable, nodules disappeared	Infiltrate cleared on repeat biopsy; if indeterminate by morphology, immunohistochemistry should be negative
PR	Regression of measurable disease and no new sites	≥ 50% decrease in SPD of up to 6 largest dominant masses (index lesions); no increase in size of other nodes (non-index lesions)  (a) FDG-avid or PET positive prior to therapy; one or more PET positive at previously involved site  (b) Variably FDG-avid or PET negative; regression on CT	≥ 50% decrease in SPD of nodules (for single nodule in greatest transverse diameter); no increase in size of liver or spleen	Irrelevant if positive prior to therapy; cell type should be specified
SD	Failure to attain CR/PR or PD	(a) FDG-avid or PET positive prior to therapy; PET positive at prior sites of disease and no new sites on CT or PET  (b) Variably FDG-avid or PET negative; no change in size of previous lesions on CT	N/A	N/A
Relapsed disease or PD	Any new lesion or increase by ≥ 50% of previously involved sites from nadir	Appearance of a new lesion(s) > 1.5 cm in any axis, ≥ 50% increase in SPD of more than one node (index lesions), or ≥ 50% increase in longest diameter of a previously identified node > 1 cm in short axis.  Lesions PET positive if FDG-avid lymphoma or PET positive prior to therapy	> 50% increase from nadir in the SPD of any previous lesions	New or recurrent involvement

Key: CR = complete remission CT = computed tomography; FDG = [18F] fluorodeoxyglucose; IWG = International Working Group; NA = Not applicable; PD = progressive disease; PET = positron-emission tomography; PR = partial remission; SD = stable disease; SPD = sum of the product of the diameters

## 4.2 Secondary Endpoints

### 4.2.1 Duration of Response (IRRC-assessed)

Duration of response (DOR) is defined as the time from first response (CR or PR) to the date of initial objectively documented progression as determined using the 2007 revised International

Working Group Criteria for Malignant Lymphoma or death due to any cause, whichever occurs first. For subjects who neither progress nor die, the DOR will be censored on the date of their last evaluable tumor assessment. Subjects who start subsequent therapy without a prior reported progression will be censored at the last evaluable tumor assessments prior to initiation of the subsequent anticancer therapy. Stem Cell Transplant will be considered as subsequent therapy. This endpoint will only be evaluated in subjects with objective response of CR or PR.

Duration of Stable Disease will also be evaluated for subjects with SD as best response. Duration of SD is defined as the time between the first dose date to the date of the first documented progression, as determined by IRRC, or death due to any cause, whichever occurs first. Subjects who neither progress nor die will be censored at the same time they will be censored for the DOR analysis.

#### **4.2.2 Complete Remission Rate and Duration (IRRC-assessed)**

The complete remission rate (CRR) is defined as the number of subjects with a BOR of CR according to the 2007 revised International Working Group Criteria for Malignant Lymphoma, based on IRRC assessment, divided by the number of treated subjects.

To further characterize CRR, the duration of CR will also be evaluated in subjects with objective response of CR. Duration of CR is defined as the time from first documentation of CR (the date of first negative FDG-PET scan or the date of first documentation of no disease involvement in the bone marrow (if required), whichever occurs later) to the date of initial objectively documented progression as determined using the 2007 IWG criteria or death due to any cause, whichever occurs first. Censoring will be applied as per DOR definition.

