5.4.1 Radiographic Assessments

Radiographic study evaluations will take place in accordance with the flow charts in Section 5.1 and Table 5.4.1-1. Baseline assessments should be performed within 28 days prior to the first dose, utilizing spiral CT or MRI. In addition to chest, abdomen, pelvis, all known sites of disease (including CNS) should be assessed at baseline. A PET scan is required at baseline for all subjects, and to confirm a complete response (CR).

On-study assessments should include chest, abdomen, and pelvis, and all known sites of disease (including CNS) and should use the same imaging method as was used at baseline.

Subjects will be evaluated for tumor response by spiral CT/MRI beginning at week 9 and continuing every 8 weeks (+/- 1 week) through the first 8 months, every 12 weeks (+/- 2 weeks) months 9-24, and then every 6 months (+/-3 weeks) thereafter until disease progression is documented or until the subject initiates a preparative regimen for allogeneic SCT or ASCT, whichever occurs earlier.

Tumor assessments for ongoing study treatment decisions will be completed by the investigator using the 2007 revised International Working Group Criteria for Malignant Lymphoma criteria. (Appendix 2)

Table 5.4.1-1: Schedule of Spiral CT-MRI Tumor Assessments			
Time On Study	Assessment Frequency	Assessment Week (day 1 of week shown)	Assessment Window
Dose 1 to 8 Months	Every 8 weeks	9, 17, 25, 33	+/- 1 week
Month 9 to 2 Years	Every 12 weeks	45, 57, 69, 81, 93	+/- 2 weeks
> 2 Years	Every 6 months	119, 145, 171+	+/- 3 weeks

Note: Once subjects discontinue study therapy by proceeding to allogeneic SCT or ASCT, they will not undergo radiographic assessments described here, but will be followed with specific schedule (see Section 5.4)

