8.3.2 Secondary Endpoint(s)

The first secondary objective will be measured by the duration of ORR (DOR) based on IRRC assessment. DOR is defined as the time from first response (CR or PR) to the date of initial objectively documented progression as determined using the 2007 revised International Working Group Criteria for Malignant Lymphoma or death due to any cause, whichever occurs first. For subjects who neither progress nor die, the DOR will be censored on the date of their last evaluable tumor assessment. Subjects who start subsequent therapy without a prior reported progression will be censored at the last evaluable tumor assessments prior to initiation of the subsequent anticancer therapy. This endpoint will only be evaluated in subjects with objective response of CR or PR.

The second secondary objective will be measured by the complete remission rate (CRR) based on IRRC assessment. The CRR is defined as the number of subjects with a BOR of CR according to the 2007 revised International Working Group Criteria for Malignant Lymphoma, divided by the number of treated subjects. The BOR is defined similarly as above. The duration of CR will only be evaluated in subjects with BOR of CR and is defined as the time from first documentation of CR (the date of first negative FDG-PET scan or the date of first documentation of no disease involvement in the bone marrow (if required), whichever occurs later) to the date of initial objectively documented progression as determined using the revised 2007 IWG response criteria for malignant lymphoma or death due to any cause, whichever occurs first. Censoring will be applied as per DOR definition.

The third secondary objective will be measured by PR rate based on IRRC assessment. It is defined as the number of subjects with a BOR of PR according to the 2007 revised IWG response criteria, based on IRRC assessment, divided by the number of treated subjects. The duration of PR will only be evaluated in subjects with BOR of PR and is defined as the time

from first documentation of PR to the date of initial objectively documented progression as determined using the 2007 revised IWG response criteria or death due to any cause, whichever occurs first. Censoring will be applied as per DOR definition.

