 - a) Typically [¹⁸F] fluorodeoxyglucose (FDG)-avid lymphoma: in patients with no pretreatment positron emission tomography (PET) scan or when the PET scan was positive before therapy, a post-treatment residual mass of any size is permitted as long as it is PET negative.
 - b) Variably FDG-avid lymphomas/FDG avidity unknown: in patients without a pretreatment PET scan, or if a pretreatment PET scan was negative, all lymph nodes and nodal masses must have regressed on computed tomography (CT) scan to normal size (≤ 1.5 cm in their greatest transverse diameter for nodes > 1.5 cm before therapy). Previously involved nodes that were 1.1 to 1.5 cm in their long axis and > 1.0 cm in their short axis before treatment must have decreased to ≤ 1.0 cm in their short axis after treatment.
2. The spleen and/or liver, if considered enlarged before therapy on the basis of a physical examination or CT scan, should not be palpable on physical examination and should be considered normal size by imaging studies, and nodules related to lymphoma should disappear. However, determination of splenic involvement is not always reliable because a spleen considered normal in size may still contain lymphoma, whereas an enlarged spleen may reflect variations in anatomy, blood volume, the use of hematopoietic growth factors, or causes other than lymphoma.
3. If the bone marrow was involved by lymphoma before treatment, the infiltrate must have cleared on repeat bone marrow biopsy. The biopsy sample on which this determination is made must be adequate (with a goal of > 20 mm unilateral core). If the sample is indeterminate by morphology, it should be negative by immunohistochemistry. A sample that is negative by immunohistochemistry but demonstrates a small population of clonal lymphocytes by flow cytometry will be considered a CR until data become available demonstrating a clear difference in patient outcome.

PR (Partial Remission)

The designation of PR requires all of the following:

1. At least a 50% decrease in the sum of the product of the diameters (SPD) of up to 6 of the largest dominant nodes or nodal masses. These nodes or masses should be selected according to all of the following: they should be clearly measurable in at least 2 perpendicular dimensions; if possible they should be from disparate regions of the body; and they should include mediastinal and retroperitoneal areas of disease whenever these sites are involved.

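### Duration of CR is dated from PET and marrow alone, leaving out the spleen/liver condition and, where PET was negative before therapy, the CT condition

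*SAP*

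**What the plan says.** SAP 4.2.2 sets the starting point in general terms: "Duration of CR is defined as the time from first documentation of CR". A parenthesis then turns this into a date: "the date of first negative FDG-PET scan or the date of first documentation of no disease involvement in the bone marrow", qualified by "involvement in the bone marrow (if required), whichever occurs later". Protocol 8.3.2 gives the same rule and adds that "The duration of CR will only be evaluated in subjects with BOR of CR".

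CR itself is defined by the 2007 IWG criteria (Protocol Appendix 2; SAP Table 4.1-1). For nodal masses there are two routes:

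- Route (a): "FDG-avid or PET positive prior to therapy; residual mass of any size permitted if PET negative".
- Route (b), for variably FDG-avid disease or a negative PET before therapy: "if a pretreatment PET scan was negative, all lymph nodes and nodal masses must have regressed on computed tomography (CT) scan to normal size".

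On either route, a spleen or liver that was enlarged before therapy must no longer be palpable and "should be considered normal size by imaging studies, and nodules related to lymphoma should disappear". Involved marrow must have cleared.

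Protocol 5.4.1 requires a PET scan at baseline in all subjects and another to confirm CR.

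**The concern.** The dating rule takes the later of two component dates, whereas CR may depend on up to four components. A negative PET can therefore set the start of CR while the spleen or liver is still abnormal or, on route (b), while nodes are still enlarged on CT. The subject is correctly counted as a CR once everything has cleared, but the clock starts earlier than that.

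The rule also does not say which PET it means. With a baseline PET in every subject, the words do not by themselves exclude a pre-dose scan.

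At stake is a named secondary endpoint, reported by cohort as a Kaplan-Meier median with 95% CI and as a range (SAP 7.5.3) in complete responders only. The range, in particular, can be set by a single misdated subject.

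**Working it through.** The plan states no figure for this point, so there is none to reproduce. The check compares the dating rule with the CR criteria and then sizes the dating error from the scan schedule.

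**Step 1. Components of CR against components of the date**

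| CR component (Appendix 2, SAP Table 4.1-1) | Applies to | In the date rule? |
|---|---|---|
| PET negative | route (a) as a criterion; all CRs as confirmation (Protocol 5.4.1) | yes, with no post-dose qualifier |
| Nodes normal on CT | route (b) only | no |
| Spleen/liver normal, nodules gone | both routes; bites where abnormal before therapy | no |
| Marrow cleared | where involved before therapy | yes, if required |

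For PET-positive or FDG-avid disease there is no CT size condition to omit. The gap there is limited to spleen and liver.

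**Step 2. What an early start does to the endpoint**

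SAP section 8 computes duration as last date − first date + 1. Starting the clock k days too early therefore adds exactly k days to that subject's duration, whether the subject has an event or is censored.

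**Step 3. Negative on-study PET, remaining condition met one scan later**

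Inputs: visits on day 1 of weeks 9, 17, 25, 33 and 45 (Protocol Table 5.4.1-1); 30.4375 days per month (SAP section 8).

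k = (later week − earlier week) × 7.

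- Weeks 9 to 17, 17 to 25, 25 to 33: 8 × 7 = 56 days; 56 / 30.4375 = 1.84 months.
- Weeks 33 to 45: 12 × 7 = 84 days; 84 / 30.4375 = 2.76 months.

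These are nominal visit dates. Assessment windows of ±1 week through week 33 and ±2 weeks afterwards widen them.

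**Step 4. Literal reading, baseline PET negative and no marrow requirement**

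Assumption: the baseline PET falls 0 to 28 days before first dose. The 28-day window is stated for CT/MRI, not expressly for PET.

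k = (week CR is first met − 1) × 7 + (0 to 28).

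- CR met at week 9: 56 to 84 days (1.8 to 2.8 months).
- Week 17: 112 to 140 days (3.7 to 4.6 months).
- Week 25: 168 to 196 days.
- Week 33: 224 to 252 days (7.4 to 8.3 months).

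**Step 5. Consistency check on the literal reading**

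DOR starts at the first CR or PR (SAP 4.2.1) and PFS at first dose (SAP 4.2.4). With a start at the baseline scan, duration of CR would exceed the same subject's DOR. It would also exceed PFS by the 0 to 28 days between scan and first dose. The literal wording therefore conflicts with the plan's other endpoints, which argues for clarifying it and against supposing that it was meant.

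**The case against.** The strongest reply is that the governing words are the first documentation of CR, and that the parenthesis only dates a CR already established under the full criteria. The analysis is limited to subjects whose best response is CR, and response designations count only from first dose (SAP 4.1). PET is used to confirm CR, and Protocol 8.5 foresees assessments that show CR before PET has confirmed it. In that sequence PET falls at or after the CT, and the later of PET and marrow is normally the date CR is complete. IRRC procedures also sit in a charter not included in these documents.

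Much of this stands. It makes early dating the exception, and it makes a baseline start an unlikely intention. It does not close the gap. The parenthesis is the only operational date given, and a programmer would code it. Duration of PR (SAP 4.2.3) starts at first documentation of PR with no such parenthesis, so the CR rule is a deliberate specification. The best-response window decides who is a complete responder, not when the clock starts. An on-study negative PET can still precede clearance of spleen or liver.

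Three stronger readings are tempting but not supported:

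- **That the rule ignores CT for all complete responders.** The CT size condition exists only on route (b).
- **That CR will in practice be dated at baseline.** This requires reading the parenthesis apart from the words it explains and from the best-response window. Such subjects may also be rare: Appendix 2 places the limit of PET detection below 1.5 cm, while entry requires a lesion above 1.5 cm.
- **That the error can only lengthen duration.** This follows if PET confirmation is itself counted as a CR condition. If a route (b) CR is taken to rest on CT alone, as in Appendix 2, a later confirmatory PET would start the clock late.

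**Conclusion.** The point holds as a definition gap of minor weight. The stated date rule does not match the plan's own CR criteria: it omits spleen and liver on both routes and CT regression on route (b), and it does not require a post-dose PET.

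Where a negative on-study PET precedes the remaining condition by one visit, CR is dated 56 days early through week 33 and 84 days early for weeks 33 to 45, at nominal visits. The larger figures for a baseline start rest on a literal reading that is probably not intended, and on the assumption that the 28-day window covers PET.

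The documents give no count of subjects who are PET-negative at baseline or whose spleen or liver clears late. The number is probably small, and the effect on the median cannot be calculated. Duration of CR is descriptive, with no hypothesis test. ORR, CRR, DOR and PFS do not use this date.

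**What to change.** In both Protocol 8.3.2 and SAP 4.2.2, replace the parenthesis with a rule to this effect: CR is dated at the first post-dose IRRC assessment at which all 2007 IWG conditions for CR applicable to that subject are met, that is, the latest of the on-study PET, CT where applicable, spleen/liver, and marrow if required. Check that the IRRC charter dates CR in the same way.

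The cost is one sentence in each document and a small programming change. The downside is that reported duration of CR may be slightly shorter.
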